8.4.2.1 Hematology

Hematology tests are to be performed according to the visit schedules outlined in Table 8-1. For details of the Hematology panel, refer to Table 8-3.

Hematology should be assessed on the scheduled day, even if study drug is being withheld.

8.4.2.2 Biochemistry

Eltrombopag administration can cause abnormal liver function and severe hepatotoxicity, which might be life-threatening.

Serum ALT, AST and bilirubin should be measured prior to initiation of eltrombopag, every 2 weeks during the dose adjustment phase and monthly following establishment of a stable dose. Abnormal serum liver tests should be evaluated with repeat testing within 3 to 5 days. If the abnormalities are confirmed, serum liver tests should be monitored until the abnormalities resolve, stabilize, or return to baseline levels. Eltrombopag should be discontinued if ALT levels increase (> 3 × ULN in patients with normal liver function, or \ge 3 × baseline or > 5 × ULN, whichever is the lower, in patients with pre-treatment elevations in transaminases) and are:

- progressive, or
- persistent for \geq 4 weeks, or
- accompanied by increased direct bilirubin, or
- accompanied by clinical symptoms of liver injury or evidence for hepatic decompensation

Biochemistry tests are to be performed according to the visit schedules outlined in Table 8-1. For details of the biochemistry panel refer to Table 8-3.

Biochemistry should be assessed on the scheduled day, even if study drug is being withheld.

Eltrombopag is highly colored and so has the potential to interfere with some laboratory tests. Serum discoloration and interference with TBIL and creatinine testing have been reported in patients taking Revolade/Promacta. If the laboratory results and clinical observations are inconsistent, evaluation of contemporaneous aminotransferase values may help in determining the validity of low TBL levels in the presence of clinical jaundice and blood urea should be evaluated in the event of an unexpectedly high serum creatinine. Re-testing using another method may also help in determining the validity of the result (Choy et al 2016).

8.4.3 Viral serology

In addition to medical history, screening assessments for hepatitis B, hepatitis C and human immunodeficiency virus (HIV) will be performed by the local laboratory according to Table 8-1.

8.4.4 Electrocardiogram

A standard 12 lead ECG will be performed at the screening visit.

Interpretation of the tracing must be made by a qualified physician and documented on the ECG CRF page. Each ECG tracing should be labeled with the study number, patient initials (where regulations permit), patient number, date, and kept in the source documents at the study site.

Clinically significant abnormalities present at screening should be reported on the Medical History CRF page. Clinically significant findings must be discussed with Novartis prior to enrolling the patient in the study. New or worsened clinically significant findings occurring after informed consent must be recorded on the AE CRF page.

Novartis	Confidential	Page 56
Amended Protocol Version 03 (Clean)		Protocol No. CETB115JDE01

Additional, unscheduled, safety ECGs may be repeated at the discretion of the investigator at any time during the study as clinically indicated. Local cardiologist ECG assessment may also be performed at any time during the study at the discretion of the investigator.

8.4.5 **Pregnancy and assessments of fertility**

All pre-menopausal women who are not surgically sterile will have pregnancy testing. Serum or urine pregnancy tests are to be performed according to the Visit Schedules outlined in Table 8-1. At screening, a serum pregnancy test should be performed regardless of the age of the patients, while, during the study, and at the end of study, urinary pregnancy tests (dipstick) are sufficient. Pregnancy testing (serum or urine) must be performed on a monthly basis while receiving study drug until study drug discontinuation. A positive pregnancy test requires immediate interruption of study treatment until the assessment is confirmed. If positive, the patient must be discontinued from the study.

Assessments of Fertility

Medical documentation of oophorectomy, hysterectomy, or tubal ligation must be retained as source documents. Subsequent hormone level assessment to confirm the woman is not of child-bearing potential must also be available as source documentation in the following cases:

- 1. Surgical bilateral oophorectomy without a hysterectomy
- 2. Reported 12 months of natural (spontaneous) amenorrhea with an appropriate clinical profile

In the absence of the above medical documentation, FSH testing is required of any female subject regardless of reported reproductive/menopausal status at screening/baseline.

8.4.6 Appropriateness of safety measurements

The safety assessments selected are standard for this indication/patient population.

8.5 Additional assessments

Bone marrow biopsies is recommended for patients > 60 years or in the presence of abnormalities and can be performed at the discretion of the investigator.

8.5.1 Clinical Outcome Assessments (COAs)

Patient reported outcomes (PRO)

Immune thrombocytopenia is associated with symptoms of fatigue, bruising, and bleeding, which can interfere with daily activities. Consequently, subjects with ITP have decreased HRQoL compared with healthy individuals. To assess patient-reported outcomes (PROs), HRQoL changes over time will be assessed using standard validated instruments.

The **Functional Assessment of Chronic Illness Therapy-Fatigue (FACIT-Fatigue)** instrument is a 13-item, easy-to-administer, validated tool used to measure an individual's level of fatigue during usual daily activities over the past 7 days (Cella and Nowinski 2002, Webster et al 2003). FACIT-Fatigue is a subscale of the FACIT measurement system, which is a validated collection of HRQoL questionnaires targeted to the management of chronic illness that are used to measure

HRQoL on multiple general and disease-specific domains. FACIT-fatigue is scored using a 4-point Likert scale (4=not at all fatigued to 0=very much fatigued) where the total possible score ranges from 0-5; higher scores represent better HRQoL (Signorovitch et al 2011). FACIT-Fatigue will be administered before any study drug administrations at the beginning of treatment and after 1, 2, 4, 12, 26, and 52 weeks and EOS (for patients with premature study withdrawal before W53D1). A minimal clinically important difference from baseline in FACIT-Fatigue score will be evaluated (Cella and Nowinski 2002). The overall total score will be evaluated;

The Medical Outcome Trust's Short-Form 36 Health Survey, Version 2 (SF-36v2), which is a validated instrument used to measure general physical and mental health status (Ware 2000), will be used to assess the impact of ITP on physical function and ability to conduct day-to-day activities. The SF-36v2 is used to measure patients' overall HRQoL via assessment of 8 domains—Physical Functioning, Role Physical, Bodily Pain, General Health, Vitality, Social Functioning, Role Emotional, and Mental Health—over the past 4 weeks or 7 days. The SF-36 is scored using norm-based scoring procedures and scores ranging from 0-100; higher scores represent better HRQoL. Two summary scores, the Physical Component Score (PCS) and the Mental Component Summary (MCS), can also be calculated.

The SF-36v2, specifically the Physical Functioning and the Role Physical domains, demonstrated good reliability and validity for measuring the proposed constructs in the ITP population (Signorovitch et al 2011). The Physical Functioning domain includes 10 items related to limitations in physical functioning and is scored using a 3-level Likert scale (1=yes, limited a lot; 2=yes, limited a little; and 3=no, not at all limited); higher scores represent less functional limitation. The Role Physical domain is used to measure to what degree physical health interferes with work/other daily activities, includes 4 items (reduction in the amount of time spent on work/other activities, accomplishing less than one would like, limitations in kind of work/other activities, and difficulty performing work/other activities), and is scored using a 5-level Likert scale (1=all of the time; 5=none of the time); lower scores represent less impact on daily activities. SF-36v2 will be administered before any study drug administrations at the beginning of treatment and after 1, 2, 4, 12, 26, and 52 weeks and EOS (for patients with premature study withdrawal before W53D1), and change from baseline will be evaluated.

The site personnel should check the questionnaire for completeness and ask the patient to complete any missing responses. The original questionnaire will be kept with the patient's file as the source document.

Completed questionnaire(s) and any unsolicited comments written by the patient should be reviewed and assessed by the investigator for responses which may indicate potential AEs or SAEs.

8.5.3 Other Assessments

The modified WHO (Kaufman et al 2015) Bleeding Scale (Page et al 2007) will be administered at every visit (refer Section 16.2).

9 Study discontinuation and completion

9.1 Discontinuation

9.1.1 Discontinuation of study treatment

Early discontinuation of study treatment for a patient occurs when study treatment is stopped earlier than the protocol planned duration, and can be initiated by either the subject or the investigator.

The investigator must discontinue study treatment for a given subject if, he/she believes that continuation would negatively impact the subject's well-being.

Study treatment must be discontinued under the following circumstances:

- Patient/guardian decision
- Pregnancy
- Use of prohibited treatment as per recommendations in the prohibited treatment section
- Any situation in which study participation might result in a safety risk to the patient
- Any laboratory abnormalities that in the judgment of the investigator, taking into consideration the subject's overall status, prevents the subject from continuing participation in the study

If early discontinuation of study treatment occurs, the investigator should make a reasonable effort to understand the primary reason for the subject's premature discontinuation of study treatment and record this information.

Subjects who discontinue study treatment or who decide they do not wish to participate in the study further should NOT be considered withdrawn from the study UNLESS they withdraw

their consent (see withdraw of informed consent section,). Where possible, they should return for the assessments indicated in the assessment schedule. If they fail to return for these assessments for unknown reasons, every effort (e.g. telephone, e-mail, letter) should be made to contact the subject/pre-designated contact as specified in the lost to follow-up section. This contact should preferably be done according to the study visit schedule.

If the subject cannot or is unwilling to attend any visits, the site staff should maintain regular telephone contact with the subject, or with a person pre-designated by the subject. This telephone contact should preferably be done according to the study visit schedule.

After study treatment discontinuation, at a minimum, in abbreviated visits, the following data should be collected at clinic visits or via telephone/email contact:

- new / concomitant treatments
- AEs/SAEs

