6.1.4 Treatment duration

Arm A: The treatment duration for all patients in Arm A (eltrombopag QD for 26 weeks + high-dose dexamethasone QD for 4 consecutive days starting at day 1 and limited to 1 cycle) will be 26 weeks (6 months) including 6 weeks tapering period. All patients who discontinue study treatment as per study design with platelet counts $\geq 30 \times 10^{9}$ /L in the absence of bleeding or use of any rescue therapy will be followed for response assessments till Week 52 after study start. Patients who relapse after eltrombopag discontinuation before Week 52 will reinitiate treatment with eltrombopag till Week 52 and will discontinue from study at Week 52. Patients with platelet counts < 30×10^{9} /L after 26 weeks of treatment with eltrombopag will continue treatment as summarized in Table 6-1 and discontinue from study at Week 52.

Arm B: The maximum duration of treatment with dexamethasone for all patients in Arm B will be 12 weeks. All patients who discontinue study treatment as per study design with platelet counts $\geq 30 \times 10^9/L$ in the absence of bleeding or use of any rescue therapy will be followed for response assessments till Week 52. Patients who relapse (platelet count $< 30 \times 10^9/L$) after dexamethasone discontinuation before Week 52 will be treated with eltrombopag as summarized in Table 6-2 and discontinue the study at Week 52. Patients with platelet count $< 30 \times 10^9/L$ after 3 cycles with dexamethasone will initiate treatment with eltrombopag and discontinue the study at Week 52.

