6.5.3 Follow-up for toxicities

Patients whose treatment is interrupted or permanently discontinued due to an AE or clinically significant laboratory value, must be followed up at least once a week (or more frequently if required by institutional practices, or if clinically indicated) for 4 weeks, and subsequently at approximately at least 4-week intervals (or more frequently if required by institutional practices, or if clinically indicated), until resolution or stabilization of the event, whichever comes first. Appropriate clinical experts such as ophthalmologist, etc. should be consulted as deemed necessary.

Patients who permanently discontinue eltrombopag for an AE or clinically significant laboratory value will be discontinued from the study and then undergo a 30-day safety follow-up.

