12.4.2 Statistical model, hypothesis, and method of analysis

The analysis of the primary endpoint will be based on the following estimand:

The population will be the Full Analysis Set;

Variable of interest: The primary endpoint is the response rate in terms of sustained response off treatment at 52 weeks, in absence of bleeding or use of rescue therapy as defined above, i.e. a composite estimand.

Intervention effect: effect of eltrombopag in combination with a short course of high-dose dexamethasone versus 1-3 cycles of high-dose dexamethasone alone at 52 weeks, regardless of adherence to randomized treatment.

Summary measure: odds ratio

The statistical hypothesis to be rejected is that the rates of patients achieving sustained response at 52 weeks are equal in both treatment groups. The corresponding alternative hypothesis is that the rates are not equal under eltrombopag combined with a short course of high-dose dexamethasone, compared to 1-3 cycles of high-dose dexamethasone monotherapy.

Let p_A and p_B denote the proportions of patients achieving sustained response off treatment for the treatment groups:

A = eltrombopag combined with a short course of high-dose dexamethasone

B = 1-3 cycles of high-dose dexamethasone "standard"

The following hypotheses will be tested:

H₀: $(p_B / (1 - p_B)) / (p_A / (1 - p_A)) = OR_{B/A} = 1$

versus H_A : $(p_B / (1 - p_B)) / (p_A / (1 - p_A)) = OR_{B/A} \neq 1$

In other words:

 H_0 : The rate of patients achieving a sustained response off treatment at 52 weeks in the eltrombopag plus a short course of high-dose dexamethasone arm is equal to the respective rate in the 1-3 cycles high-dose dexamethasone monotherapy "standard" arm (corresponding to equal odds).

 H_A : The rate of patients achieving a sustained response off treatment at 52 weeks in the eltrombopag plus a short course of high-dose dexamethasone arm is higher than the respective rate in the 1-3 cycles of dexamethasone monotherapy "standard" arm.

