#### 2.5.3 Handling of missing values/censoring/discontinuations

If patient's platelet assessment for evaluating the primary endpoint are missing, they will be assessed as non-responder. Patients dropping out early will be considered as early discontinuation or not evaluable, will be considered in the analysis set as non-responders. Thus, missing values are not expected for the primary analysis.

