#### 2.5.4 Supportive analyses

Novartis

Reasons for non-response are assessed during the Data Review Meeting and are categorized into these distinct categories:

- 1. Initial response but lost later on, or bleeding, or rescue medication before treatment discontinuation
- 2. Initial response but treatment not discontinued
- 3. Initial response but after treatment discontinuation rescue needed
- 4. Initial response but after treatment discontinuation bleeding
- 5. Initial response but platelet count decreased <30 after treatment discontinuation
- 6. Initial response but response data are missing until W53
- 7. No response at all
- 8. No response data at all

If several reasons apply, the reason that applied first was determined to obtain distinct classes. A frequency table was presented for these reasons of non-response.

Sensitivity analyses and supportive analyses will be conducted in order to provide evidence that the results seen from the primary analysis are robust.

The impact of the analysis assumptions on the result of sustained response off treatment will be assessed as well by repeating the logistic regression model using different populations and ways to handle missing data. These includes:

Using the treatment policy estimand "sustained response based on platelet count only" a) which is defined as maintenance of a platelet count  $\geq 30 \times 10^{9}$ /l starting from cycle 1, 2 or 3 (DEX), or start of tapering at week 20 (ETB+DEX), until Week 53, i.e. no matter if intercurrent events such as bleeding, treatment discontinuation or reinitiation, or rescue treatment occurred. For this estimand the population is used: Patients of the FAS population

b) Using the treatment policy estimand b) for the population: FAS population who completed the study at least until Week 53

Data defining the primary outcome of sustained response off treatment will be further reported descriptively to give the full picture. This will include:

- Platelet counts at treatment discontinuation: sample statistics
- Frequency of patients with complete response at treatment discontinuation; defined as a) platelet count  $\geq 150 \times 10^{9/1}$ 
  - b) platelet count >  $100 \times 10^{9/1}$
  - c) platelet count  $\geq 50 \times 10^{9/1}$
- Timepoint of reaching platelet count  $\geq 150 \times 10^{9}$ /l: Kaplan Meier estimates and curve, censored with date of last study medication/last visit

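### Protocol 9.1.1's minimum data for patients who stop treatment early omit platelet counts, so a patient followed only at that minimum can fail the primary endpoint but never meet it

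*Protocol*

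**What the plan says.** Protocol 9.1.1 covers treatment stopped earlier than planned. Such patients "should NOT be considered withdrawn from the study UNLESS they withdraw" consent, and the first request is for full follow-up: "Where possible, they should return for the assessments indicated in the assessment schedule". That schedule (Table 8-1) has hematology and the WHO Bleeding Scale at every visit.

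The section then gives a fallback: "After study treatment discontinuation, at a minimum, in abbreviated visits, the following data should be collected at clinic visits or via telephone/email contact". Two items follow: new or concomitant treatments, and AEs/SAEs. The floor covers abbreviated clinic visits as well as remote contact.

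Response (protocol 12.4.1) requires platelets ≥ 30 × 10⁹/L, no bleeding of Grade II or more and no rescue therapy, at all visits to Week 52. The estimand in 12.4.2 is stated "regardless of adherence to randomized treatment". For patients with missing platelet assessments, SAP 2.5.3 says "they will be assessed as non-responder", and protocol 12.4.3 has the same effect. The treatment-policy analysis in SAP 2.5.4 is to apply "no matter if intercurrent events such as bleeding, treatment discontinuation or reinitiation, or rescue treatment occurred".

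Patients who stop as the design intends are handled separately in protocol 6.1.4: they "will be followed for response assessments till Week 52 after study start".

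**The concern.** The endpoint is measured off treatment, and the estimand claims to apply whatever the adherence. That requires platelet counts after an early stop, and the floor lets a site meet the protocol without any. A patient who stops early, keeps consent, is seen only at abbreviated visits and holds platelets above 30 under routine care is then recorded as a non-responder because no count reached the database.

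At stake is the estimated response rate in each arm and the odds ratio between them. With about 24 patients and descriptive reporting, those estimates are the trial's result.

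**Working it through.** **1. The plan's own figures.** Inputs from protocol 12.8.1: 30% versus 65%, two-sided 5%, 90% power, 1:1.

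Uncorrected n per arm = (1.960·√(2·0.475·0.525) + 1.282·√(0.30·0.70 + 0.65·0.35))² / 0.35² = 40.7, so 41.

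With continuity correction: (40.7/4)·(1 + √(1 + 4/(40.7·0.35)))² = 46.2, so 47, as stated.

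Power at 12 per arm, with the same correction: Φ[(0.35 − 1/12 − 1.960·√(0.49875/12)) / √(0.4375/12)] = Φ(−0.70) = 24.3%, matching the stated 24%. The design effect of 35 points and the 12 per arm used below are thus the plan's own.

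**2. The floor against the endpoint.**

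| Needed to score response | In the 9.1.1 floor? | Result at the floor |
|---|---|---|
| Platelets ≥ 30 at all visits to Week 52 | No | Missing, so non-responder |
| No bleeding ≥ Grade II | Event yes, as an AE; WHO grade no | AEs are graded by CTCAE 5.0 (10.1.1); the trial's bleeding instrument is the modified WHO scale (8.5.3) |
| No rescue therapy | Yes, under treatments | Rescue recorded: failure by definition (6.2.3) |

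Every route through the table ends in non-response.

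**3. Whether another provision supplies the counts.**

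- 8.4.2.1 requires scheduled hematology while drug is withheld. It does not amend the floor for permanent early stops.
- 10.2.1 requires weekly platelet counts for 4 weeks after eltrombopag stops, which does not reach Week 52 for an early stopper.
- 6.1.4 secures Week 52 response follow-up only for planned stops.

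**4. Whether a planned analysis recovers them.** SAP 2.5.4(a) disregards treatment discontinuation but still needs counts up to Week 53. Analysis (b) is restricted to patients who completed to Week 53. Neither supplies a count that was not collected. Protocol 12.4.4 names multiple imputation as a possibility; the SAP's list does not include it.

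**5. Size, as an illustration.** One patient at 12 per arm: 1/12 = 8.3 points. Two in one arm: 2/12 = 16.7 points, and 16.7/35 = 48% of the design effect.

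The documents give no rate, so assume a share d of would-be responders is scored as failure for missing counts. The observed rate is then p(1 − d).

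| d, Arm A | d, Arm B | Rate A | Rate B | Difference | OR (B/A) |
|---|---|---|---|---|---|
| 0 | 0 | 65% | 30% | 35 points | 0.23 |
| 20% | 20% | 52% | 24% | 28 points | 0.29 |
| 20% | 0 | 52% | 30% | 22 points | 0.40 |
| 5% | 20% | 61.75% | 24% | 37.75 points | 0.20 |

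At 12 per arm, d = 20% in Arm A is 0.20·0.65·12 = 1.6 patients. The effect can be understated or overstated, depending on which arm loses more data.

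**The case against.** The strongest reply is that the plan does ask for the count. Full visits are the first request, patients stay in the study, and the two-item list is only a fallback. This stands. A reader might infer that the primary endpoint cannot be scored for anyone who stops treatment. The documents do not support that: early stoppers who attend the schedule can be scored, and planned stoppers are followed to Week 52.

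A reader might also infer that bleeding is lost along with platelets. It is not. Bleeding events go on the AE form (8.3.2), and AEs are in the floor. The endpoint text does not name the grading scale, so what is missing is the WHO grade, not the event.

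Nor is non-response an unforeseen default. Both documents state the rule, and SAP 2.5.4 has separate reasons for missing data: reason 6 (initial response, then data missing) and reason 8 (no response data). A reader can partly see the problem from that table. This shows the loss but does not prevent it.

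The affected group may be small. The patient must stop early, keep consent, miss full visits, and have neither rescue nor a qualifying bleed. Under protocol 6.5.3, patients who permanently stop eltrombopag for an AE or laboratory value "will be discontinued from the study and then undergo a 30-day safety follow-up". That conflicts with 9.1.1 and the two must be reconciled. It is a separate point, but read literally it shrinks the group further.

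Finally, a single latest count would not show maintenance at all visits, so a fix limited to that might change no classification. This is correct, and the fix below allows for it.

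**Conclusion.** The point holds in a limited form. For early stoppers followed only at the 9.1.1 minimum, data collection does not support the stated estimand: they can be counted as failures but not as responders, and no analysis in the SAP restores the information. For early stoppers who attend full visits there is no defect.

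The 8.3 points per patient at 12 per arm is arithmetic, not evidence of how many patients are affected. A reader might infer that the loss falls mainly on Arm A, because eltrombopag runs for 26 weeks and has its own liver stopping rules, while Arm B receives 1–3 four-day courses. That is plausible, but the documents give no early-stop rate by arm, so the direction of bias is open.

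After Amendment 3 all analyses are descriptive, so the consequence is for the estimates and their interpretation, not for a confirmatory test. Severity: minor to moderate.

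**What to change.** 1. In protocol 9.1.1, add to the minimum list all local or routine-care platelet counts since the last contact, with dates, and the WHO bleeding grade since the last contact.
2. In the SAP, state that each documented count is used for the scheduled visit it falls nearest to, for both the primary endpoint and the treatment-policy analysis. Visits with no count stay under the existing missing-data rule, so response becomes possible without being presumed.
3. Report by arm how many non-responders are so classified only because of missing data, using reasons 6 and 8 of SAP 2.5.4.

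The cost is protocol and SAP wording, one eCRF entry, and requests to outside practices for results. No new blood draw is needed. Laboratories are already local, protocol 8.4.2 foresees values from an outside laboratory, and 8.3.1 allows extra counts from clinical routine. If follow-up has already closed, item 3 can still be done at analysis.
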